5.4 Randomisation Criteria and Stratification

Subjects will be randomised into the study provided they have satisfied all subject selection criteria.

Subjects will be stratified according to their maximum baseline Schiff sensitivity score of the two selected teeth (sensitivity score of 2 or 3). Randomisation numbers will be assigned in each stratum in ascending numerical order as each subject is determined to be fully eligible. The stratification factor will give rise to two strata.

- **Stratum 1:** Maximum Schiff=2. These are subjects with maximum baseline Schiff sensitivity score of 2 for the 2 selected ‘test teeth’.
- **Stratum 2:** Maximum Schiff=3. These are subjects with the maximum baseline Schiff sensitivity score of 3 for the 2 selected test teeth.

5.5 Lifestyle Considerations

5.5.1 Oral Care Restrictions

Eligible subjects will be asked to stop using their regular oral care products, and will only be allowed to use the oral care products provided from Screening for the duration of the study. Use of dental floss will be for the removal of impacted food only.

Subjects will not be permitted to chew gum.

Prior to study visit days (Visits 2 to 4) subjects will be asked to refrain from all oral hygiene procedures for at least 8 hours prior to their appointment in order to standardise oral hygiene

practices. Subjects will be sent a WeChat reminder the day before their appointment reminding them of this.

5.5.2 Meals and Dietary Restrictions

A subject must not eat or drink (except water) for at least 2 hours before Visits 2 to 4. Small sips of room-temperature water will be permitted to take medications and relieve a dry mouth within 1 hour before their visit.

5.5.3 Alcohol

Subjects will be requested to refrain from excessive alcohol consumption for 24 hours before each visit. If, in the opinion of the Investigator, the subject has consumed an excessive amount of alcohol they will be withdrawn from the study.

5.5.4 Contraception

No drug is being utilised in this clinical study, the study products are commercialised toothpastes in China, and are regulated as General Goods. Therefore, pregnancy testing and contraceptive requirements are not deemed necessary for this study.

5.6 Screen Failures

Screen failures are defined as subjects who consent to participate in the clinical study but are not subsequently randomised. To ensure transparent reporting of screen failure subjects, a minimal set of screen failure information will include demography, screen failure details (e.g. withdrawal of consent), eligibility criteria, any protocol deviations and any adverse events or incidents as applicable.

Individuals who do not meet the criteria for participation in this study (screen failure) may not be re-screened.

5.7 Sponsor's Qualified Medical Personnel

Contact information for the sponsor's appropriately qualified dental personnel for the study is documented in the Study Contact List located in the investigator study master file held at the study site.

The contact number is only to be used by investigational staff seeking advice on medical/ dental questions or problems in the event that the established communication pathways between the investigational site and the study team are not available.

The contact number is not intended for direct use by study subjects. To facilitate access to appropriately qualified medical/dental personnel on study-related medical/dental questions or problems, subjects will be provided with a contact card. The contact card will provide, as a

Property of GSK Consumer Healthcare - Confidential

May not be used, divulged, published or otherwise disclosed without the consent of GSKCH

SOP-208661 Clinical Protocol Template v6.0

Page 28 of 85

minimum, protocol identifiers, the subject's study identification number, contact information for the investigational site, and contact details in the event that the investigational site cannot be reached to provide advice on a medical question or problem identified by a healthcare professional other than the investigator.

5.8 Rater/Clinical Assessor Qualifications

The clinical examiner(s) responsible for Schiff and tactile assessments will be dentally qualified and trained in the clinical assessments of DH, using both the air syringe (Schiff sensitivity scale) and yeaple probe (Tactile threshold). To minimise assessment variability, where possible the same examiner will be responsible for a given clinical assessment from Screening until the end of the study.

To manage logistics at the clinical study site, additional dentally qualified examiners who have not trained in the clinical assessments of DH will be permitted to conduct OHT/OST assessments and those screening procedures that do not use the air syringe (Schiff sensitivity scale) and yeaple probe (Tactile threshold).

6 INVESTIGATIONAL/STUDY PRODUCTS

For the purposes of this study, per International Conference on Harmonization (ICH) guidelines, and GSK policy, study intervention is defined as any investigational intervention(s), marketed product(s), placebo, or medical device(s) intended to be administered to a study participant according to the study protocol.

6.1 Investigational/Study Product Supplies

The following investigational/study products will be supplied by the Clinical Supplies Department, GSK CH or designated vendor:

Table 6-1 Investigational Product Supplies

Investigational Product	Test Product	Reference Product (Negative Control)	Reference Product (Positive Control)
Product Name	Sensodyne Sensitivity & Gum (Chrysanthemum); Chinese commercialised toothpaste containing 0.454% SnF ₂	Crest Cavity Protection Fresh Lime (1150ppm fluoride as NaF); Chinese commercialised daily fluoride dentifrice	Sensodyne Repair and Protect; Chinese commercialised dentifrice containing 5.0% w/w calcium sodium phosphosilicate

Property of GSK Consumer Healthcare - Confidential

May not be used, divulged, published or otherwise disclosed without the consent of GSKCH

SOP-208661 Clinical Protocol Template v6.0

Pack Design	Carton of 4 over-wrapped tubes	Carton of 4 over-wrapped tubes	Carton of 4 over-wrapped tubes
Dispensing Details	One carton – baseline visit	One carton – baseline visit	One carton – baseline visit
Product Master Formulation Code (MFC)	Commercial Product CCI [REDACTED]	Commercial Product	Commercial Product CCI [REDACTED]
Usage Instructions	Apply a full ribbon of toothpaste on the head of the toothbrush provided. Brush teeth for 1*-timed minute, followed by brushing of the qualifying sensitive teeth. Following brushing rinse once with 10 ml of water from the rinsing cup provided.	Apply a full ribbon of toothpaste on the head of the toothbrush provided; brush teeth for 1*-timed minute. Following brushing rinse once with 10 ml of water from the rinsing cup provided.	Apply a full ribbon of toothpaste on the head of the toothbrush provided; brush teeth for 1*-timed minute. Following brushing rinse once with 10 ml of water from the rinsing cup provided.
Route of Administration	Oral topical	Oral topical	Oral topical
Return Requirements	All used/unused samples to be returned	All used/unused samples to be returned	All used/unused samples to be returned

*Following toothbrushing and/or rinsing subjects may also conduct a discretionary tongue clean using the provided toothbrush, but this is not a study requirement.

Table 6-2 Acclimatisation Product Supplies

	Acclimatisation Product
Product Name	Crest Cavity Protection Fresh Lime; Chinese commercialised daily fluoride dentifrice (1150ppm fluoride as NaF)
Pack Design	Carton of 2 over-wrapped tubes

	Dispensing Details	One carton – Screening visit
	Product MFC	Commercial Product
	Usage Instructions	Apply a full ribbon of toothpaste on the head of the toothbrush provided; brush teeth for 1*-timed minute. Following brushing rinse once with 10 ml of water from the rinsing cup provided.
	Route of Administration	Oral topical
	Return Requirements	All used/unused samples to be returned

*Following toothbrushing and/or rinsing subjects may also conduct a discretionary tongue clean using the provided toothbrush, but this is not a study requirement.

Table 6-3 Sundry Items

Item	Supplied By	Pack Design	Dispensing Details	Return/Disposal Details	
				Used Samples	Unused Samples
Lion Thin Bristle Chinese commercialised Toothbrush	GSK CH or designated vendor	Individual commercial pack – 3 per subject	1 at screening for use with acclimatisation product 1 at baseline for use with investigational product 1 at Visit 3.	Destroy at site using site disposal procedures	Return
Countdown Timer	GSK CH or designated vendor	Individual commercial pack – 1 per subject	Screening visit	Subject to keep or destroyed at site using site disposal procedures	Return

Rinsing cups	GSK CH or designated vendor	N/A	Screening visit and baseline	Subject to keep or destroyed at site using site disposal procedures	Return
Plastic bags	GSK CH or designated vendor	N/A	Screening visit and baseline	Subject to keep or destroyed at site using site disposal procedures	Return

Detailed instructions for the return of study product/study supplies for the accountability checks and subsequent destruction which will be provided by GSK CH during the study in time for study close out visit.

6.1.1 Dosage Form and Packaging

The test product, negative and positive controls, acclimatisation product and toothbrush will be sourced from China.

All dentifrices in this study will be presented to the clinical study site in tubes that have been overwrapped in white vinyl to obscure any branding on the commercial packs with a study label affixed. The contents of the label will be in accordance with all applicable regulatory requirements and will be the responsibility of the Global Clinical Supplies Department, GSK CH. Each subject will receive a sufficient number of tubes to cover usage during the treatment phase.

All sundry items will be supplied in their commercial packaging for dispensing by study staff as required.

Care should be taken with the supplied products and their labels so that they are maintained in good condition. It is important that all labels remain intact and legible for the duration of the study. Subjects should be instructed to not remove or deface any part of the study label.

All products supplied are for use only in this clinical study and should not be used for any other purpose.

6.1.2 Preparation and Dispensing

Study products will be prepared and/or dispensed by qualified unblinded site personnel according to the dosage and administration instruction. To help mitigate against unblinding the same personnel responsible for preparing and/or dispensing will also be responsible for reviewing subject's brushing video's.

Property of GSK Consumer Healthcare - Confidential

May not be used, divulged, published or otherwise disclosed without the consent of GSKCH

SOP-208661 Clinical Protocol Template v6.0

Page 32 of 85

Subjects will be assigned to products in accordance with the randomisation schedule generated by an approved GSK CH vendor, prior to the start of the study, using validated software.

Study product will be dispensed by qualified unblinded site personnel. These staff members will not be involved in any safety, efficacy assessments or other aspects of the study that could be influenced by the knowledge of product a subject has been assigned to use. An additional member of site staff should ensure the dispensing procedures are completed accurately. The investigational products will be dispensed in blinded fashion to the subject.

A record of product dispensing to each subject will be maintained in the dispensing log; completion of the dispensing procedure will be recorded in the case report form (CRF).

6.2 Administration

A record of the administration of the study products will be kept using a dispensing log and will be recorded in the CRF.

Subjects will be instructed to brush with their assigned dentifrice according to the product use instructions provided to the subject. Subjects will receive a brushing instruction/diary sheet. This will outline the brushing instructions and will be used to record each brushing occasion during the treatment period. Subjects will also be asked to note any missed brushings, and to use the diary to record any changes in medications, or new medications, or to diet. To ensure that subjects understand the dose of dentifrice to be used, staff will demonstrate what is meant by a 'full ribbon' (i.e. covering the length of the toothbrush head) and provide detailed oral hygiene instruction during the supervised toothbrushing in agreement with the study schedule and product usage instructions.

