4.3 Justification for Dose and Regimen

The dosage regimen of twice daily (morning and evening) brushing with a full ribbon of dentifrice on the supplied toothbrush for 1-timed minute will be the same for all subjects, and has been selected based on the minimum amount of time required to achieve DH efficacy in previously conducted clinical studies containing a SnF₂ dentifrice ([Parkinson, 2011](#); [Makin, 2013](#)). Additional focused brushing of the identified 'test teeth' has been included for the Test dentifrice to ensure that the 'test teeth' are being treated, and to standardise treatment and facilitate monitoring of compliance. These instructions for use are aligned with the current product usage instructions in the USA, as determined by the US FDA Monograph for OTC Oral Health Care Drug Products; "*Apply at least a 1-inch strip of the product onto a soft bristle toothbrush. Brush teeth thoroughly for at least 1 minute twice a day (morning and evening) or as recommended by a dentist or doctor. Make sure to brush all sensitive areas of the teeth*" ([FDA, 1991](#)). Focused brushing of the sensitive teeth is not required for the Negative control as it is not marketed as an anti-sensitivity dentifrice, and therefore the usage instructions reflect those of a standard daily fluoride dentifrice, and do not require the sensitive areas of the teeth to be brushed. The usage instructions of the positive control dentifrice containing 5% w/w

Property of GSK Consumer Healthcare - Confidential

May not be used, divulged, published or otherwise disclosed without the consent of GSKCH

SOP-208661 Clinical Protocol Template v6.0

calcium sodium phosphosilicate are aligned with the usage instructions that were used in GSK CH clinical studies where long-term DH efficacy was demonstrated in China ([GSK CH clinical studies: RH01422 and RH01748](#)).

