6.5 Blinding and Allocation/Randomisation

All subjects will be centrally randomised to one of the study arms using an Interactive Response Technology (IRT). Before the study is initiated, training, login information and directions for the IRT will be provided to the clinical study site. Study products will be dispensed according to the instruction received through the IRT at the appropriate study visits.

Returned study products should not be re-dispensed to any subject.

This study is described as examiner-blind (the subjects, investigator and clinical examiner(s) will be blinded to product received). The study statistician, other employees of the Sponsor

(including the Clinical Research Scientist (CRS)) and vendors acting on behalf of the sponsor, who may influence study outcomes will also be blinded to product allocation.

To ensure the examiner remains blinded throughout the study, staff involved in the preparation and dispensing of study products will work in a separate area. The examiner is not permitted in any area where study product is stored, dispensed, or in use. Examiners must also not have any visibility, or access to subject brushing video's. The same personnel responsible for preparing and/or dispensing will also be responsible for reviewing subject's brushing video's, and the study examiners will not be permitted in the area where these video's are viewed.

Subjects will be instructed not to remove study products from the opaque bags provided outside of the dispensing room, while at the study site. They will also be instructed not to discuss the use of their study products with any of the study examiners. Dispensing staff will not be involved in any efficacy/safety assessment procedures during the study.

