Subjects will also be requested to bring their study products to each clinical study site visit, where a member of the clinical study team will weigh the returned dentifrice. If treatment use is deemed to be outside of the pre-defined acceptable range, subjects will be re-educated on the correct dosage amount. Where the amount of dentifrice used is outside of the pre-defined allowable range, a protocol deviation will be recorded in the CRF and subjects will be re-educated on the correct dose. In this study the pre-defined range will be calculated as the expected weight of dentifrice used for the treatment window ([Section 12.3.7.1](#)). The amount of dentifrice used during each treatment period will be recorded in a source document and later transcribed to the CRF.

At the same visit subjects will be asked to conduct a supervised and timed brushing according to the product usage instructions. Confirmation of supervised brushing per protocol will be captured in the CRF. Any deviations from the product usage instructions will be captured as a protocol deviation in the CRF, and subjects will be reminded of the correct directions for use.

A paper diary will also be supplied to promote compliance and to capture details of daily product use throughout the study period. Subjects may also record additional information such as AEs or medications used. Any additional details relevant to efficacy or safety should be reviewed by the investigator (or suitably qualified designee) with the subjects and transcribed to the CRF as appropriate.

The number of any missed or additional applications or doses will be captured as protocol deviations and transcribed from the diary to the CRF. Subjects will be re-instructed in the correct usage requirements and diary completion as needed.

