8.4 Diary Review

The diary should be reviewed at every visit by the investigator, or suitably qualified designee, and the subject. Any subject comment captured in the diary which is considered an adverse

event will be assessed and reported as per the defined procedure in this protocol. Adverse event reporting procedures are summarised in [Adverse Event and Serious Adverse Events](#).

Any additional comments relating to medications/treatments provided in the diary will be reviewed by the investigator or medically qualified designee with the subject and entered into the CRF as appropriate.

Additional and missed product applications will be considered deviations from the protocol and will be recorded as a protocol deviation in the CRF.

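### The combined brushing-instruction and diary sheet can show a blinded diary reviewer who is on the test product, and no blinding safeguard covers it

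*Protocol*

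**What the plan says.** Protocol 6.2 describes one document with two uses: "Subjects will receive a brushing instruction/diary sheet. This will outline the brushing instructions and will be used to record each brushing occasion".

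The instructions differ by arm. Table 6-1 tells test subjects: "Brush teeth for 1*-timed minute, followed by brushing of the qualifying sensitive teeth". Both control arms have the timed minute and the rinse only: "brush teeth for 1*-timed minute. Following brushing rinse once with 10 ml of water from the rinsing cup provided". Section 4.3 shows that the difference is intended: "Focused brushing of the sensitive teeth is not required for the Negative control as it is not marketed as an anti-sensitivity dentifrice". The same section aligns the positive control with the instructions used in its own earlier studies.

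Section 8.4 sets the review: "The diary should be reviewed at every visit by the investigator, or suitably qualified designee, and the subject". Section 6.7 likewise sends diary details bearing on efficacy or safety to the investigator or a designee.

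Section 6.5 states that "the subjects, investigator and clinical examiner(s) will be blinded to product received".

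**The concern.** Taken together, these sections can give a person declared blinded a paper that shows whether the subject is on the test product. The protocol already treats brushing behaviour as unblinding: examiners may not see the brushing videos, and only the unblinded dispensing staff review them. The sheet would state in writing the same extra step that a video shows, but it gets no such protection.

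Two things are at stake. The investigator or a medically qualified designee judges adverse-event causality (10.5.2), and the investigator classifies events as oral or non-oral (12.3.4). Schiff, the primary endpoint, is scored by an examiner from the subject's observed reaction (9.2.2), so it depends on the examiner not knowing the arm. Once the sheets are in use, a loss of blinding cannot be undone.

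**Working it through.** The point itself involves no calculation, so the check is mainly a comparison of sections.

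1. **Does the sheet carry the arm's own instructions?** Section 6.2 says that it outlines the brushing instructions. For a test subject, these include the sensitive-teeth step. The items issued at Visit 2 (8.2.1.9 and the Schedule of Activities) include a diary but no separate instruction leaflet. The sheet is not in the documents, so this step is an inference.

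2. **When can it reveal the arm?** The diary brought to Visit 2 covers acclimatisation, when every subject has the same instructions (Table 6-2). Only the treatment-period sheet, reviewed at Visits 3 and 4, can reveal anything. It separates test from control, but not one control from the other.

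3. **Who may read it?**
   - The investigator: named in 8.4, blinded under 6.5.
   - An unblinded dispenser: not compatible with 6.1.2 and 6.5, which keep dispensing staff out of safety assessments. Review under 8.4 includes recognising and assessing adverse events.
   - A designee who neither dispenses nor examines: permitted. This would keep the examiner blind.
   - An examiner acting as designee: not excluded by 5.8, 6.5, 8.4 or 9.2.

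4. **Do the safeguards reach the sheet?**

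| Safeguard | Section | Covers the sheet? |
|---|---|---|
| White overwrap on tubes | 6.1.1 | No |
| Separate storage, dispensing and use areas | 6.5 | No |
| Videos kept from examiners | 6.5 | No |
| Opaque bags | 6.5 | Products only |
| Subjects not to discuss product use with examiners | 6.5 | Speech only |

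5. **Is the diary read before scoring?** Diary review has no stated place in the visit order. Concomitant medication comes first at Visits 3 and 4 and Schiff later (8.2.2), and subjects note medication changes in the diary (6.2). The diary may therefore be open before scoring, but the protocol does not say so.

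6. **How many reviews?** With equal arms, 195 / 3 = 65 test subjects, and 65 × 2 visits = 130 reviews at most. With the 60 expected completers, 60 × 2 = 120. This counts reviews of a sheet that may reveal the arm. It does not count unblindings.

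7. **How sensitive is the primary test to biased scoring?** The plan's own figure first: with 60 per group, difference 0.3 and SD 0.501, the standard error is 0.501 × √(2/60) = 0.0915. The exact two-sided 5% t-test then has 90.2% power, which agrees with the stated 90%. Next, assume no true effect and a scoring bias b between test and negative control. The values of b are assumptions and do not come from the documents.

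| b (Schiff points) | b / 0.0915 | Chance of p < 0.05 |
|---|---|---|
| 0.05 | 0.55 | 8% |
| 0.10 | 1.09 | 19% |
| 0.15 | 1.64 | 37% |
| 0.20 | 2.19 | 58% |

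The table shows why examiner blinding deserves care. It does not estimate what the sheet would cause.

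**The case against.** The strongest reply is that nobody reading these documents has seen the sheet. Section 6.2 also mentions product use instructions provided to the subject, so the full text could be a separate document and the sheet generic. This stands as a limit on certainty. It does not settle the matter, because no section says that the sheet is generic, detachable or hidden from the reviewer.

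The second reply is that 6.5 names the investigator and the examiners separately, and 8.4 gives diary review to the investigator or a designee. This also stands. A reader might infer that the Schiff examiner is unblinded, or that the primary result is biased by some fraction of the 0.3 design difference. The documents support neither. The route to Schiff needs the diary reviewer to examine or to inform the examiner, and any percentage would rest on an invented misgrading rate.

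A reader might also infer that examiner blinding is the only protection claimed. It is not: subjects are described as blinded (6.5), tubes are overwrapped (6.1.1), dispensing to the subject is blinded (6.1.2), and an acclimatisation period is meant to limit placebo and no-treatment effects (4.2).

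Finally, a deviation description naming the sensitive-teeth step could point to the test arm at the blinded data review, since SAP 4.1.2 lists such descriptions. The specific details and the assessment process are left to two plans that are not in the documents, so the wording is unknown. The reach is limited too: the primary population is mITT, and the per-protocol analysis runs only if the populations differ by more than 10% (SAP 4.1.3).

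**Conclusion.** The concern holds as a conflict between Protocol 6.2, 6.7 and 8.4 on one side and 6.5 on the other. If the sheet outlines each subject's own instructions, as 6.2 indicates, the treatment-period sheet tells its reviewer at Visits 3 and 4 whether the subject is on test. That is up to about 130 test-arm reviews, or 120 among expected completers.

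Adverse-event causality is directly exposed when the investigator reviews the diary. Exposure of Schiff is conditional on the reviewer examining or informing the examiner. The protocol does not rule this out, but nothing shows that it happens. The size of any bias cannot be derived from the documents. The conclusion rests on one inference, the content of an unseen sheet.

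**What to change.** - **Protocol 6.2:** use one diary form, identical in all arms, with no usage instructions. Put the instructions on a separate card, issued by the unblinded dispensing staff and kept in the opaque bag with the product. The usage instructions themselves stay as they are.
- **Protocol 6.5 and 8.4:** state that the card must not be shown to the investigator or examiners, and that Schiff and tactile examiners do not review diaries.
- **Deviation listing for the blinded review:** at most, keep out wording that reveals the arm, while retaining each deviation's type and importance. Withholding all detail until database lock would go too far, because important deviations and exclusions are decided before lock (Protocol 12.2.2, SAP 4.1.2).

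The cost is reprinting the sheets and a short wording change.
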